- ▶ **Survey 3**: (12-weeks after delivery): Participants will be contacted via SMS text or email to ask about follow up with a primary care physician and chronic hypertension. Participants will receive a \$20 gift card for completion of this survey.

OUTCOMES

Primary Outcomes: The outcome for the R21 and listed on ClinicalTrials.gov is the proportion of patients with a blood pressure recorded in the office at 7-10 days postpartum (**BPinperson**). It is not hypothesized that the primary outcome varies by the blood pressure control intervention but will vary by the blood pressure management intervention.

Secondary Outcomes: We will examine three categories of secondary outcomes (**Table 3**). *Hypertension control and adverse events* includes measures of blood pressure control and events potentially associated with poor blood pressure control such as severe maternal morbidity (SMM) and hospital readmission. Given that our intervention tests different models of care, we will assess *health care utilization* associated with these models including adherence to in-person and remote blood pressure monitoring, medication use, attendance at scheduled visits, and unscheduled visits to an urgent care or emergency room.

We will also examine a variety of *patient-reported outcome measures* especially satisfaction with care. HDP carries not only a risk of long-term health sequelae, but also post-traumatic stress disorder, depression, and anxiety.^{92,93} In a review of patients' experiences with HDP, the potential for worsening or chronic hypertension was associated increased feelings of anxiety and loss of agency.⁹⁴ We hypothesize that augmented remote monitoring and tighter blood pressure control, both individually and in combination, will improve postpartum blood pressure control within the first six weeks postpartum. We also hypothesize that participants, especially Black participants, will find the results of these interventions satisfying and acceptable as they provide a nexus of agency during otherwise stressful life events. Observed reductions in blood pressure provide more frequent and immediate feedback to participants relative to other meaningful outcomes such as SMM or hospital readmission. We also acknowledge the possibility that patients also could find frequent observation of blood pressures and tighter parameters to be burdensome or increase anxiety about health status.

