While postpartum patient-reported outcome measures have been developed and validated to study inpatient recovery, lack of consensus exists regarding optimal measures of outpatient recovery.⁹⁵ In a recent systematic review of validated measures used to assess three domains or more of outpatient postpartum recovery, three measures were identified but all had significant limitations.⁹⁶ The authors conclude that assessment may be better achieved using existing methods such as those endorsed by the Patient-Reported Outcomes Measurement Information System initiative (PROMIS).⁹⁶ Therefore, we selected validated PROMIS and NIH Toolbox measures related to depression, anxiety, and social support. Because experience of being listened to or being ignored and dismissed are central drivers of Black women's pregnancy and postpartum experience and health outcomes,^{38,39} we emphasize outcomes related to communication during and satisfaction with clinical encounters such as the Communication Assessment Tool -Team (CAT-T) and the Mothers on Respect index (MORi), a scale developed to assess the nature of respectful patient-provider interactions and their impact on a person's sense of comfort, behavior, and perceptions of racism or discrimination.

VARIABLE NAME	DESCRIPTION	DERIVATION	VALUE
7-10 Day Outcomes			
BPinperson710	BP recorded in person	None	1=yes 0=no
BPMremote710	Any BP recorded remotely	A systolic BP (d710sbp_remote) or a diastolic BP (d710dbp_remote) value is present	1=yes 0=no
BPanyp710	Any BP recorded in person or remotely	If BPinperson710 = 1 or BPMremote710=1	1=yes 0=no
SBP710	SBP value Selected by the following hierarchy: 1) in person SBP, 2) remote SBP - If multiple remote BP values were submitted, selected the SBP from day 8 and average the values.	SBP710 = d710sbp_inperson if d710sbp_inperson is present. If d710sbp_inperson is absent, then use d710sbp_remote.	Continuous
DBP710	DBP value Selected by the following hierarchy: 1) in person DBP, 2) remote DBP - If multiple remote BP	DBP710 = d710dbp_inperson if d710dbp_inperson is present. If	Continuous

	values were submitted, selected the DBP from day 8 and average the values.	d710dbp_inperson is absent, then use d710dbp_remote.	
SBP710_bin	SBP value \geq 140	SBP710 \geq 140	1=yes 0=no
DBP710_bin	DBP value \geq 90	DBP710 \geq 90	1=yes 0=no
ANYhigh_bin	Any BP value \geq 140/90	SBP710 \geq 140 OR DBP710 \geq 90	1=yes 0=no
SBPsevere710_bin	SBP value \geq 160	SBP710 \geq 160	1=yes 0=no

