DBPsevere710_bin	DBP value \geq 110	DBP710 \geq 110	1=yes 0=no
ANYsevere_bin	Any BP value \geq 160/110	SBP710 \geq 160 OR DBP710 \geq 90	1=yes 0=no
dcp_medstart	Any medication started between discharge through week 6 after delivery	n/a	1=yes 0=no
dcpp_medstart	Days postpartum that medication was started	n/a	Continuous
readmit	Hospital readmission	n/a	1=yes 0=no

The two co-primary outcomes are mean systolic blood pressure (SBP) and diastolic blood pressure (DBP) recorded in-office (**Table 3**). In a secondary analysis, we will also include mean blood pressure measurements reported via augmented remote monitoring among women who do not attend in-office visits. The third co-

primary outcome is proportion of participants with sustained severe hypertension during the first 6 weeks postpartum defined as a SBP ≥ 160 or a DBP ≥ 110 on two occasions at least 15 minutes apart.

Secondary Outcomes

We will examine three categories of secondary outcomes (**Table 3**). *Hypertension control and adverse events* includes measures of blood pressure control and events potentially associated with poor blood pressure control such as severe maternal morbidity (SMM) and hospital readmission. Given that our intervention tests different models of care, we will assess *health care utilization* associated with these models including adherence to in-person and remote blood pressure monitoring, medication use, attendance at scheduled visits, and unscheduled visits to an urgent care or emergency room.

Table 3: Study outcomes and time frame for assessment

Hypertension Outcomes		
Blood pressure control (Primary Outcome)	Mean SBP assessed in-office and through all methods	7-10 days
Blood pressure control (Primary Outcome)	Mean DBP assessed in-office and through all methods	7-10 days
Severe hypertension (Primary Outcome)	SBP ≥ 160 or DBP ≥ 110 on two occasions 15 minutes apart and less than 4 hours apart	6 weeks
Hospital readmission	Readmission for hypertension management after delivery discharge	3 weeks
Severe maternal morbidity	Center for Disease Control criteria	6 weeks
Health Care Utilization		
Blood pressure assessment	Proportion who report at least one BP reading post delivery	7-10 days
Medication use	Proportion requiring and/or initiating antihypertensive medications	6 weeks
Urgent care visit	Visit to obstetric triage or an emergency department for hypertension	3 weeks

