Aim 1 Analytic Approach: Our primary analysis will examine the independent effect of the interventions (blood pressure goals and monitoring approach) on the primary outcomes. While randomized trials greatly reduce confounding, they do not eliminate it, and covariate adjustment enhances statistical power. Balance in participant's demographic and clinical characteristics across the four groups (control + 3 interventions) will be compared using the Mann-Whitney *U* test for continuous variables and Chi squared test for categorical variables. Characteristics that exhibit differences across groups and potential confounding variables such as race, socioeconomic status, and medical comorbidities will be considered as adjusting covariates in the subsequent regression analysis. Multiple linear regression with ordinary least square estimates (OLS) will be used to compare the SBP and DBP primary outcomes across four interventions with a binary variable for the monitoring intervention (standard vs augmented), a binary variable for the blood pressure goal intervention (standard 150/100 and tight 140/90) and an interaction term between the two binary variables for the combined interventions. A negative value for two main effects of interventions indicates better blood pressure control using individual interventions alone than the standard of care. A negative value for the interaction effect indicates better blood pressure control using combined intervention than individual intervention alone. Post hoc analysis of variance (ANOVA) can be conducted to assess the overall effect of each individual interventions (with 2 degree of freedom) and the overall intervention effects (with 3 degree of freedom). Although OLS does not require normality assumption for outcomes and residuals, extreme outliers might result in potential bias. In this case, a non-parametric model (e.g. proportional odds model) will be considered. This analysis will be repeated allowing the primary outcome to include mean blood pressures reported via augmented remote monitoring among women who do not attend in-office visits. Multiple logistic regression will be conducted for binary outcomes including the severe hypertension primary outcome, hypertension secondary outcomes and healthcare utilization secondary outcomes. The same main effects and interaction effects for interventions specified for the linear regression model will be included with negative values for the log-odds ratio indicating improved outcomes in the intervention groups. Linear regression with OLS will be used for patient-reported secondary outcome measures in a similar fashion as SBP and DBP primary outcomes. Given the prospective design and dedicated personnel, we anticipate little missing covariate data. In case there are more than 1% participants with missing data in the analysis, multiple imputation will be conducted as sensitivity analysis. All outcomes will be analyzed as intent-to-treat.

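### The primary SBP/DBP variable is defined inconsistently, and the in-office analysis has no stated method for women without an office reading, although having one is expected to differ by monitoring arm

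*Combined protocol and SAP*

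**What the plan says.** Four places in the combined protocol and SAP bear on which SBP/DBP value is primary.

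- **OUTCOMES, co-primary paragraph:** "The two co-primary outcomes are mean systolic blood pressure (SBP) and diastolic blood pressure (DBP) recorded in-office". A secondary analysis adds "mean blood pressure measurements reported via augmented remote monitoring among women who do not attend in-office visits".
- **Aim 1 Analytic Approach:** consistent with that. After the main model, "This analysis will be repeated allowing the primary outcome to include mean blood pressures reported via augmented remote monitoring".
- **Table 3:** the row marked as primary reads "Mean SBP assessed in-office and through all methods", with a matching row for DBP.
- **7-10 Day Outcomes variable table:** SBP710 takes the in-person value first. "If d710sbp_inperson is absent, then use d710sbp_remote"; DBP710 works the same way. Neither is labelled primary or secondary. The in-person fields appear only as inputs to them.

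On who will have an office reading, OUTCOMES (Primary Outcomes) gives the registered outcome as the proportion with an office blood pressure at 7-10 days and adds: "It is not hypothesized that the primary outcome varies by the blood pressure control intervention but will vary by the blood pressure management intervention". No direction is given. The visit is requested for everyone (Randomization and Procedures before Hospital Discharge).

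On adjustment and missing data, the Aim 1 section says: "Characteristics that exhibit differences across groups and potential confounding variables such as race, socioeconomic status, and medical comorbidities will be considered as adjusting covariates". Baseline blood pressure is not in that list. It then says "we anticipate little missing covariate data", plans multiple imputation as a sensitivity analysis if more than 1% of participants have missing data, and states that all outcomes are analysed by intention to treat.

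**The concern.** An analyst working from the narrative would fit the primary model to in-office readings. One working from the variable table would fit it to SBP710/DBP710, which is the analysis that the narrative calls secondary. Table 3 does not settle which is meant.

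The choice matters for the monitoring contrast. An in-office mean exists only for women who attended, and the plan itself expects attendance to differ by monitoring arm. That contrast is therefore not a comparison of all randomised women, despite the intention-to-treat statement.

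The fallback does not repair this evenly. Remote-arm women log every reading in the app. Provider-arm women (Intervention A) report only abnormal readings or symptoms, and to their own clinician. Fill-in therefore comes essentially from one side and mixes home with office readings. The cuff is to be checked at the first follow-up appointment, which women without an office reading may have missed.

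If attendance is also related to blood pressure, the estimated effect of remote monitoring combines a change in blood pressure with a difference in who was measured.

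**Working it through.** **1. The plan's own power figure.** Inputs from Power and Sample Size Considerations: 250 v 500 women, 80% power, alpha 0.05 (two-sided assumed), SD 17.2 (SBP) and 11.9 (DBP).

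(1.960 + 0.842) × √(1/250 + 1/500) = 2.80 × 0.0775 = 0.217 SD

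This matches the stated 0.22. In mmHg it is 3.73 SBP and 2.58 DBP, which round to the stated 4 and 3. The power arithmetic is not in question.

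**2. The definitions side by side.**

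| Place | Value used | Label |
|---|---|---|
| Co-primary paragraph | in-office | primary |
| Aim 1 Analytic Approach | in-office, then repeated with remote | primary, then repeat |
| Table 3 | in-office and all methods | primary |
| SBP710/DBP710 | in-office, else remote | none |

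**3. Illustrative size of selection bias.** The documents give no attendance rate by arm and no link between attendance and blood pressure, so everything here except the SDs is assumed: attendance of 50 to 70%, a gap of 10 to 20 points in either direction, correlation ρ of 0.2 to 0.3 between blood pressure and propensity to attend, a normal model and no true effect. Bias is remote minus provider.

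Let λ(p) = φ(z_p)/p. This gives 0.497 at 70%, 0.644 at 60% and 0.798 at 50%.

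- In-office: bias = SD × ρ × (λ_remote − λ_provider). Example, 70% provider and 50% remote, ρ = 0.2: 17.2 × 0.2 × (0.798 − 0.497) = 1.04 mmHg.
- Fallback, with a fraction f of remote-arm non-attenders filled in and no provider-arm fill-in: replace λ_remote by φ(z_p)(1 − f)/[p + f(1 − p)]. Same example, f = 0.5: 0.399 × 0.5/0.75 = 0.266, so 17.2 × 0.2 × (0.266 − 0.497) = −0.79 mmHg.

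SBP bias in mmHg, for ρ = 0.2 / 0.3:

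| Attendance, provider / remote | In-office | Fallback, half filled | Fallback, all filled |
|---|---|---|---|
| 70% / 60% | +0.51 / +0.76 | −0.88 / −1.32 | −1.71 / −2.56 |
| 70% / 50% | +1.04 / +1.55 | −0.79 / −1.19 | −1.71 / −2.56 |
| 60% / 70% | −0.51 / −0.76 | −1.51 / −2.27 | −2.22 / −3.32 |
| 50% / 70% | −1.04 / −1.55 | −2.04 / −3.06 | −2.74 / −4.12 |

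A negative ρ reverses every sign, and ρ = 0 gives zero throughout. In-office DBP bias is 11.9/17.2 of the SBP figure, about 0.4 to 1.1 mmHg in absolute size.

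**4. Home against office readings.** Home readings would be f(1 − p)/[p + f(1 − p)] of remote-arm values: 18% (70% attending, half filled) to 50% (50% attending, all filled). Each 1 mmHg of mean home-office difference would move the unadjusted fallback contrast by about 0.18 to 0.50 mmHg, even with ρ = 0.

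**5. What baseline adjustment does.** I simulated ordinary least squares on attenders with pre-randomisation SBP as covariate (assumed correlation 0.5 with the outcome) over the same attendance rates and ρ. In-office bias is about 0 if attendance depends on that baseline value. It is about 0.4 to 1.2 mmHg in absolute size if attendance depends on the outcome itself.

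**6. The other contrast.** The plan does not expect office readings to vary by blood pressure goal. With equal attendance and equal ρ the two λ terms cancel, so the goal contrast is little affected.

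**The case against.** The plan is not silent on women without an office reading. It sets out a repeat analysis that adds their remote values, and the imputation sentence is worded for missing data in general, although it follows a remark about covariates. A reader might infer that no method is planned at all; the documents do not support that. What stands is narrower: neither back-up is part of the primary in-office analysis, the imputation is not said to cover outcomes and has no stated model, and the substitution is one-sided.

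Table 3 can be read as listing both planned analyses in one row rather than redefining the primary. That is fair, and it makes the entry ambiguous rather than wrong, but an ambiguous primary row still needs settling. Likewise SBP710/DBP710 suit the repeat analysis, and the in-office fields already exist by name. The fault is an unstated role, not a faulty variable.

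The covariate list is introduced as examples, so baseline blood pressure is not excluded. It is also not committed to, and selection by observed imbalance remains.

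The strongest objection concerns bias. The plan says only that attendance will vary. A reader might infer that remote-arm women attend less, but Table 2 has the program manager in the remote arms remind women about all visits, which could raise attendance. A reader might also infer that the in-office and fallback analyses err in opposite directions and so bracket the truth. The last two rows of the table show both erring the same way. Neither inference is supported.

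**Conclusion.** The inconsistency stands on the text alone: the narrative and the Aim 1 section define an in-office primary, Table 3 is ambiguous, and the only derived continuous variables follow another rule with no stated role. It also stands that the in-office monitoring contrast conditions on an event expected to differ by arm, that the primary analysis has no stated missing-outcome method, and that baseline blood pressure is not named. Confidence in these points is high.

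Confidence in the presence, direction and size of bias is low. Selection bias needs attendance to be related to blood pressure, which the documents do not state. Under the assumed rates and correlations, in-office bias is about 0.5 to 1.6 mmHg SBP in absolute size against the 4 mmHg target. The fallback bias differs from it and may have the same or the opposite sign. These figures show that the issue could matter, not that the trial result will be biased.

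The registered office-reading outcome and the stated 0.22 SD are unaffected, and the blood-pressure-goal contrast is little affected. This should be fixed before analysis.

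**What to change.** 1. **Name one primary variable.** Reconcile the co-primary paragraph, the Aim 1 section, Table 3 and the variable table. If in-office is meant, use d710sbp_inperson and d710dbp_inperson, and keep SBP710/DBP710 for the repeat analysis.
2. **Pre-specify covariates.** Put inpatient SBP/DBP recorded before randomisation (which the overview places on postpartum day one) and race, the stratification factor, in the least-squares model in place of selection by observed imbalance. Type of hypertensive disorder is optional.
3. **Cover the missing outcome.** State that the multiple imputation includes missing office readings and uses baseline blood pressure. Add a simple arm-specific delta analysis, because baseline adjustment does not remove bias if attendance depends on the outcome itself. The shift in the all-randomised contrast per 1 mmHg of delta in one arm is 1 − attendance: 0.5 mmHg at 50%, 0.3 at 70%.
4. **Label the analysis that adds remote values** as not comparable between monitoring arms, because those values come essentially from the remote arms only.

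The cost is SAP wording, one chart-extracted blood pressure per woman and a little more analysis work. The imputation rests on missing at random given baseline, which cannot be verified; the delta analysis probes it.

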We propose a comprehensive management program for postpartum patients with HDP who are at risk for severe maternal morbidity and mortality. Our program will emphasize three key components: 1) self-monitoring of blood pressures with app-based reporting connected to our electronic health record, 2) blood pressure management directed by a program navigator with guideline and physician support and 3) facilitated transitions of care to primary care clinicians for hypertension management. We will randomize 1400 patients with HDP on postpartum day one with follow up through 3 months postpartum. Primary outcome will be blood pressure control at 2 weeks postpartum. Secondary outcomes include identification and treatment of severe blood pressures, severe maternal morbidity, postpartum and primary care visit attendance, and multiple patient-reported outcome measures. All outcomes will be stratified by race (Black and non-Black) to evaluate disparities and by tight versus usual blood pressure control to evaluate the impact of strict postpartum blood pressure control on outcomes. We hypothesize that a comprehensive postpartum HDP management program will improve hypertension control for all patients and reduce disparities that affect Black patients, and that stricter blood pressure control will be associated with fewer adverse outcomes.

OBJECTIVE

Specific Aim 1: To assess whether augmented remote blood pressure monitoring and tight blood pressure control, both individually and in combination, improve blood pressure control and the frequency of severe hypertension in the first 2 weeks postpartum.

Specific Aim 2: To test whether these interventions narrow the existing Black/non-Black inequity in postpartum outcomes such as blood pressure control and severe hypertension.

ELIGIBILITY CRITERIA

Inclusion Criteria

1. Age ≥ 18 years
2. Diagnosed with a Hypertensive Disorder of Pregnancy (HDP), which includes chronic hypertension, preeclampsia, gestational hypertension, HELLP Syndrome (Hemolysis, Elevated Liver enzymes, Low Platelets), or eclampsia (O10, O11, O13, O14, O15, O16)

Exclusion Criteria

1. Not able or willing to receive electronic surveys
2. Deemed inappropriate for study enrollment by bedside nurse
3. Non-English speaking
4. Discharge on postpartum day 6 or greater
5. Contraindication to ACOG-recommended hypertension control (i.e. chronic kidney disease, stroke)

SCREENING

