APPENDIX B: Epic MyHealth Message for Intervention #1 (Standard Control / In-Office Monitoring)

Dear Ms. [last name],

Thank you for being part of the Vanderbilt Fourth Trimester (V4) study. The V4 study will help us learn how to better care for women with high blood pressure in pregnancy.

You have been assigned to the following interventions:

1. Blood pressure goal: <150/100

From discharge through 6 weeks postpartum, we recommend that your blood pressure be less than 150 mmHg systolic (top number) and less than 100 mmHg diastolic (bottom number). If either the top or the bottom blood pressure is higher than the target, your obstetric provider may consider starting or changing medications.

2. Blood pressure monitoring: Obstetric Provider

- You will be given an appointment to have your blood pressure checked in the office within 10 days of delivery. Usually you receive a MyHealth message about the appointment.
- For the first 2 weeks after delivery, you should check your blood pressure twice a day
- For weeks 3 to 6, you should check your blood pressure once a day
- If your blood pressures are over the goal above, contact your obstetric provider

3. Preeclampsia Danger Signs

Seek medical attention within an hour if you have any of the following:

- Blood pressure of 160 mmHg systolic (top number) or 110 mmHg diastolic (bottom number) after two blood pressure checks at least 15 minutes or more apart and within 4 hours
- A persistent headache that does not go away with rest, eating, or Tylenol
- Spots in your vision or difficulty seeing
- Difficulty breathing
- Persistent and worsening pain in your belly especially in the mid-upper or right-upper areas

4. Long-term Care

High blood pressure in pregnancy often goes away after delivery, but in some people it stays. Even if it goes away, having high blood pressure in pregnancy can make you higher risk for high blood pressure or heart disease later in life. You should see a primary care provider or cardiologist within 3 months after delivery to discuss ways to improve your heart health and to monitor your blood pressure. Be sure to tell your provider that you had high blood pressure in pregnancy.

Instructions for checking your blood pressure

1. Wait at least 30 minutes after smoking, eating, drinking caffeine (coffee, tea, soda), or exercising.
2. Sit comfortably at a table with both feet on the floor and your arm resting on the table, palm up.

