APPENDIX C: Epic MyHealth Message for Intervention #2 (Tight Control / OB Provider Monitoring)

Dear Ms. [last name],

Thank you for being part of the Vanderbilt Fourth Trimester (V4) study. The V4 study will help us learn how to better care for women with high blood pressure in pregnancy.

You have been assigned to the following interventions:

1. Blood pressure goal: <140/90

From discharge through 6 weeks postpartum, we recommend that your blood pressure be less than 140 mmHg systolic (top number) and less than 90 mmHg diastolic (bottom number). If either the top or the bottom blood pressure is higher than the target, your obstetric provider may consider starting medications or changing your dose of medication.

2. Blood pressure monitoring: Obstetric Provider

- You will be given an appointment to have your blood pressure checked in the office within 10 days of delivery. Usually, you receive a MyHealth message about the appointment.
- For the first 2 weeks after delivery, you should check your blood pressure twice a day
- For weeks 3 to 6, you should check your blood pressure once a day
- If your blood pressures are over the goal above, contact your obstetric provider

3. Preeclampsia Danger Signs

Seek medical attention within an hour if you have any of the following:

- Blood pressure of 160 mmHg systolic (top number) or 110 mmHg diastolic (bottom number) after two blood pressure checks at least 15 minutes or more apart and within 4 hours
- A persistent headache that does not go away with rest, eating, or Tylenol
- Spots in your vision or difficulty seeing
- Difficulty breathing
- Persistent and worsening pain in your belly especially in the mid-upper or right-upper areas

4. Long-term Care

High blood pressure in pregnancy often goes away after delivery, but in some people it stays. Even if it goes away, having high blood pressure in pregnancy can make you higher risk for high blood pressure or heart disease later in life. You should see a primary care provider or cardiologist within 3 months after delivery to discuss ways to improve your heart health and to monitor your blood pressure. Be sure to tell your provider that you had high blood pressure in pregnancy.

Instructions for checking your blood pressure

1. Wait at least 30 minutes after smoking, eating, drinking caffeine (coffee, tea, soda), or exercising.
2. Sit comfortably at a table with both feet on the floor and your arm resting on the table, palm up.

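### The severe-hypertension co-primary has no stated start later than delivery, so read literally it counts events before randomisation, and possibly inpatient events before the assigned goals begin, which shrinks the relative effect and costs power.

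*Combined protocol and SAP*

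**What the plan says.** The OUTCOMES section of the combined protocol and SAP defines the third co-primary as the "proportion of participants with sustained severe hypertension during the first 6 weeks postpartum". Table 3 describes it as "SBP ≥ 160 or DBP ≥ 110 on two occasions 15 minutes apart and less than 4 hours apart" and gives six weeks as the time frame. Neither place sets a start at consent, randomisation or discharge, or excludes earlier readings.

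The overview ahead of the OBJECTIVE section states: "We will randomize 1400 patients with HDP on postpartum day one with follow up through 3 months postpartum". The exclusion criterion "Discharge on postpartum day 6 or greater" leaves women discharged as late as postpartum day 5 eligible.

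The documents differ on when the assigned goal begins:

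- Participant messages (Appendices B to E) start it at discharge. Appendix B says "From discharge through 6 weeks postpartum, we recommend that your blood pressure be less than 150 mmHg systolic" and Appendix C says "From discharge through 6 weeks postpartum, we recommend that your blood pressure be less than 140 mmHg systolic".
- Blood pressure Control, sections (C) and (D), gives targets with no start.
- Table 2 counts its monitoring weeks from delivery.
- Provider messages (Appendices F to I) state the target with no start.

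Some other outcomes are tied to discharge. The derived variable for starting medication is "Any medication started between discharge through week 6 after delivery", and Table 3 counts readmission only after the delivery discharge. Specific Aim 1 asks about "the frequency of severe hypertension in the first 2 weeks postpartum", a shorter period than the co-primary covers.

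**The concern.** The outcome is yes or no per woman. A woman with two qualifying severe readings before randomisation is already an event, and nothing in her assigned arm can change that. The same holds for a woman with a qualifying pair in hospital after randomisation, if her goal and monitoring start only at discharge.

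Randomisation should spread such events evenly over the arms, so the risk is not a spurious difference. It is that both factors look weaker in relative terms and the comparison has less power than stated. The power paragraph applies the 57% reduction to the whole 10.2% institutional rate, which is described over the same six-week postpartum period. If part of that rate cannot be prevented, the planning figure is optimistic.

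**Working it through.** **Inputs.** From Power and Sample Size Considerations and Table 6: control rate p1 = 0.102; relative risk 0.43 (57% reduction); 250 standard-care against 500 intervention women, so k = 2; alpha 0.05; power 80%. Two-sided testing is assumed, because the plan does not say.

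**Reproducing the plan's figure.** p2 = 0.102 × 0.43 = 0.0439; d = 0.102 − 0.0439 = 0.0581; pooled p = (0.102 + 2 × 0.0439)/3 = 0.0632.

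n′ = [1.960·√(p(1−p)(1+1/k)) + 0.842·√(p1(1−p1) + p2(1−p2)/k)]² / d² = 222.2

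With continuity correction, n = (n′/4)·[1 + √(1 + 2(1+1/k)/(n′d))]² = 247.3, rounded up to 248 (plan: 250). Power at 250 against 500 is 80.4%. The stated 80% therefore reproduces, provided every counted event can be prevented.

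**Dilution model.** Let f be the share of control events that assignment cannot affect. The documents do not give f; 10% to 40% is assumed. With relative risk 0.43 on the remainder:

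- Counted from delivery: control 0.102; intervention 0.102·[f + 0.43(1−f)]; apparent reduction 0.57(1−f).
- Counted from discharge, taking f as everything before discharge: control 0.102(1−f); intervention 0.43 × 0.102(1−f); reduction stays 57%.
- Absolute difference in both: 0.57 × 0.102 × (1−f).

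| f | Apparent reduction from delivery | Absolute difference, either window | Power from delivery | Power from discharge |
|---|---|---|---|---|
| 0 | 57% | 5.8 points | 80% | 80% |
| 10% | 51% | 5.2 | 70% | 76% |
| 20% | 46% | 4.7 | 58% | 70% |
| 30% | 40% | 4.1 | 46% | 64% |
| 40% | 34% | 3.5 | 34% | 57% |

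Power uses the formula above at 250 against 500. At the factorial margins, 500 against 500, f = 20% gives 74% from delivery and 85% from discharge.

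**Effect needed.** For 57% to appear overall, the reduction in preventable events must be 0.57/(1−f): 63%, 71%, 81% and 95% for f = 10%, 20%, 30% and 40%. Above f = 43% it is impossible.

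**Detectable effect on the shorter window.** Solving the same formula for p2 at 80% power with control rate 0.102(1−f) gives detectable reductions of about 60%, 63%, 67% and 71% for the same four values.

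**Limit of the model.** It treats a woman with an early event as adding nothing later. If she also has a qualifying pair after discharge and is counted for it, the discharge-window rate exceeds 0.102(1−f), so that column is on the cautious side.

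**The case against.** The text fixes the end of the window and leaves the start unsaid. A reader might infer that the plan positively intends to count inpatient and pre-consent readings. It does not say so. The derived-variable table has no six-week sustained-severe variable and no data source for one. If only outpatient readings were collected, early events would drop out unaided. This stands, and it is why the point is an undefined start with a literal reading that does harm.

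A reader might also infer that no inpatient event can be prevented because the goals apply only after discharge. That rests on the participant messages alone. Sections (C) and (D), Table 2 and the provider messages do not support it, and cuffs and instructions are handed out before discharge. This stands too: exposure between randomisation and discharge is unclear. Only events before randomisation are unpreventable on every reading.

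Three further points stand. The missing start is not peculiar to this outcome, since severe maternal morbidity and medication use in Table 3 lack one as well. Discharge occurs after randomisation and its timing could depend on assignment, so under the stated intent-to-treat analysis randomisation is the more natural start. And the OUTCOMES section elsewhere names an in-office reading at 7-10 days as the registered primary outcome, so the standing of this endpoint is itself unsettled.

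None of this answers the core point. As written, the window opens before randomisation, and the power statement assumes that every event in it can be prevented.

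**Conclusion.** The concern holds in this limited form. The co-primary needs a stated start, and on its literal wording it includes events that no assignment could affect. The consequence is a smaller relative effect and lower power. It is not a false-positive bias, and under the model the absolute difference does not change.

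The size cannot be fixed from the documents, because the 10.2% is not split by timing. At an assumed f of 20%, a true 57% reduction shows as 46% and power is 58% instead of 80%. The certain part of f, events before randomisation, may be well below the share before discharge. The figures also assume a two-sided continuity-corrected test, 250 against 500 women and equal early event rates across arms.

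It would be wrong to conclude that a discharge start restores the planned power: at f = 20% it gives 70%. The difference between Aim 1's two weeks and the outcome's six is a separate inconsistency and adds nothing to the dilution argument. The six-week end agrees with the hypothesis in the OUTCOMES section.

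**What to change.** 1. Define the co-primary as sustained severe hypertension with a qualifying pair of readings from randomisation through week 6. Record severe hypertension before randomisation as a baseline variable, shown by arm.
2. Pre-specify a version starting at delivery discharge that counts any qualifying pair after discharge, whether or not there was an earlier inpatient pair.
3. Report a day-14 version, so that the period named in Aim 1 is covered.
4. Reconcile the passages on when the assigned goals begin: the participant messages, sections (C) and (D), Table 2 and the provider messages.
5. Split the institutional 10.2% by timing, if those data allow, and restate the planning rate and detectable effect on the chosen window.

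The cost is outcome wording, a date restriction and a rerun of the power calculation. The date restriction assumes that qualifying readings are dated, which the documents do not state. The price is a lower baseline rate and a less favourable stated detectable effect: on a discharge window, about a 60% to 71% reduction for f of 10% to 40%, against the 57% now quoted. A randomisation start would lower the rate by less.
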